13. DEFINITION OF END OF TRIAL

13.1. End of Trial in All Participating Countries

End of trial in all participating countries is defined as last subject last visit (LSV).

14. SPONSOR DISCONTINUATION CRITERIA

Premature termination of this study may occur because of a regulatory authority decision, change in opinion of the IRB/EC, or investigational product safety problems, or at the discretion of Pfizer. In addition, Pfizer retains the right to discontinue development of crisaborole at any time.

If a study is prematurely terminated, Pfizer will promptly notify the investigator. After notification, the investigator must contact all participating subjects and the hospital pharmacy (if applicable) within 7 days. As directed by Pfizer, all study materials must be collected and all CRFs completed to the greatest extent possible.

15. PUBLICATION OF STUDY RESULTS

15.1. Communication of Results by Pfizer

Pfizer fulfills its commitment to publicly disclose clinical trial results through posting the results of studies on www.clinicaltrials.gov (ClinicalTrials.gov), the European Clinical Trials Database (EudraCT), and/or www.pfizer.com, and other public registries in accordance with applicable local laws/regulations.

In all cases, study results are reported by Pfizer in an objective, accurate, balanced, and complete manner and are reported regardless of the outcome of the study or the country in which the study was conducted.

www.clinicaltrials.gov

Pfizer posts clinical trial US Basic Results on www.clinicaltrials.gov for Pfizer-sponsored interventional studies (conducted in patients) that evaluate the safety and/or efficacy of a Pfizer product, regardless of the geographical location in which the study is conducted. US Basic Results are submitted for posting within 1 year of the primary completion date (PCD) for studies in adult populations or within 6 months of the PCD for studies in pediatric populations.

PCD is defined as the date that the final subject was examined or received an intervention for the purposes of final collection of data for the primary outcome, whether the clinical study concluded according to the prespecified protocol or was terminated.

EudraCT

Pfizer posts European Union (EU) Basic Results on EudraCT for all Pfizer-sponsored interventional studies that are in scope of EU requirements. EU Basic Results are submitted for posting within 1 year of the PCD for studies in adult populations or within 6 months of the PCD for studies in pediatric populations.

www.pfizer.com

Pfizer posts Public Disclosure Synopses (clinical study report synopses in which any data that could be used to identify individual patients has been removed) on www.pfizer.com for Pfizer-sponsored interventional studies preferably at the same time the US Basic Results document is posted to www.clinicaltrials.gov.

15.2. Publications by Investigators

Pfizer supports the exercise of academic freedom and has no objection to publication by the principal investigator (PI) of the results of the study based on information collected or generated by the PI, whether or not the results are favorable to the Pfizer product. However, to ensure against inadvertent disclosure of confidential information or unprotected inventions, the investigator will provide Pfizer an opportunity to review any proposed publication or other type of disclosure of the results of the study (collectively, “publication”) before it is submitted or otherwise disclosed.

The investigator will provide any publication to Pfizer at least 30 days before it is submitted for publication or otherwise disclosed. If any patent action is required to protect intellectual property rights, the investigator agrees to delay the disclosure for a period not to exceed an additional 60 days.

The investigator will, on request, remove any previously undisclosed confidential information before disclosure, except for any study- or Pfizer product-related information necessary to the appropriate scientific presentation or understanding of the study results.

If the study is part of a multicenter study, the investigator agrees that the first publication is to be a joint publication covering all investigator sites, and that any subsequent publications by the PI will reference that primary publication. However, if a joint manuscript has not been submitted for publication within 12 months of completion or termination of the study at all participating sites, the investigator is free to publish separately, subject to the other requirements of this section.

For all publications relating to the study, the institution will comply with recognized ethical standards concerning publications and authorship, including Section II - "Ethical Considerations in the Conduct and Reporting of Research" of the Uniform Requirements for Manuscripts Submitted to Biomedical Journals, <http://www.icmje.org/index.html#authorship>, established by the International Committee of Medical Journal Editors.

Publication of study results is also provided for in the CSA between Pfizer and the institution. In this section entitled **Publications by Investigators**, the defined terms shall have the meanings given to them in the CSA.

If there is any conflict between the CSA and any attachments to it, the terms of the CSA control. If there is any conflict between this protocol and the CSA, this protocol will control as to any issue regarding treatment of study subjects, and the CSA will control as to all other issues.

Appendix 1. Abbreviations

This following is a list of abbreviations that may be used in the protocol.

Abbreviation	Term
AD	Atopic Dermatitis
AR	Autoregressive
ADSI	Atopic Dermatitis Severity Index
AE	Adverse Event
ALT	Alanine Aminotransferase
AM	Morning
AST	Aspartate Aminotransferase
BID	Twice Daily
β-hCG	Beta Human Chorionic Gonadotrophin
BP	Blood Pressure
BPO	Benzoyl Peroxide
BSA	Body Surface Area
%BSA	Percent Body Surface Area
cAMP	Cyclic Adenosine Monophosphate
CI	Confidence Interval
CIOMS	Council for International Organizations of Medical Science
CK	Creatine Kinase
Cmax	Maximum Observed Plasma Concentration
CDLQI	Children's Dermatology Life Quality Index
CMH	Cochran-Mantel-Haenszel test
CRF	Case Report Form
CSA	Clinical Study Agreement
CSR	Clinical Study Report
C-SSRS	Columbia Suicide Severity Rating Scale
CT	Clinical Trial
CTA	Clinical Trial Application
DFI	Dermatitis Family Impact Questionnaire
DILI	Drug-Induced Liver Injury
DLQI	Dermatology Life Quality Index
DU	Dispensable Unit
EASI	Eczema Area And Severity Index
EASI75	Eczema Area And Severity Index $\geq 75\%$ improvement from Baseline
EC	Ethics Committee
EC50	Half Maximal Effective Concentration
eCRF	Electronic Case Report Form
E-DMC	External Data Monitoring Committee
EDP	Exposure During Pregnancy
ePRO	Electronic patient reported outcome

Abbreviation	Term
EU	European Union
EudraCT	European Clinical Trials Database
CCI	[REDACTED]
FAS	Full Analysis Set
FDA	Food And Drug Administration
FSH	Follicle Stimulating Hormone
GCP	Good Clinical Practice
GGT	Gamma-Glutamyl Transferase
HRQOL	Health-Related Quality Of Life
HTA	health technologies assessment
CCI	[REDACTED]
IB	Investigator's Brochure
ID	Identification
ICH	International Council For Harmonisation
IND	Investigational New Drug Application
INR	International Normalized Ratio
IP	Investigational Product
IRB	Institutional Review Board
IRT	Interactive Response Technology
IWR	Interactive Web Response
ISGA	Investigator'S Static Global Assessment
IUD	Intrauterine Devicem
LFT	Liver Function Test
LSLV	Last Subject Last Visit
MMF	Mycophenolate Mofetil
MMRM	mixed model repeated measure
CCI	[REDACTED]
MUSE	Maximal Use Systemic Exposure
N/A	Not Applicable
NRI	Non Responder Imputation
NRS	Numeric Rating Scale
OCT	Optical Coherence Tomography
CCI	[REDACTED]
PCD	Primary Completion Date
PD	Pharmacodynamics(S)
PDE-4	Phosphodiesterase-4
CCI	[REDACTED]
PI	Principal Investigator
PK	Pharmacokinetic
PKA	Protein Kinase A

Abbreviation	Term
PM	Evening
PMA	Phorbol 12-myristate 13-acetate
CCI	
PKA	Protein Kinase A
PPAS	Per Protocol Analysis Set
PRO	Patient Reported Outcome
PRN	As Needed
PT	Prothrombin Time
PUVA	Psoralen–UV-A
QD	Once Daily
QoL	Quality of Life
SAE	Serious Adverse Event
SAP	Statistical Analysis Plan
SC	stratum corneum
SRSD	Single Reference Safety Document
SSIN	Subject Screening Identification Number
SUSAR	Suspected Unexpected Serious Adverse Reaction
TEAE	Treatment Emergent Adverse Event
TBili	Total Bilirubin
TCI	topical calcineurin inhibitor
TCS	topical corticosteroid
TEWL	Transepidermal Water Loss
Tmax	Time to Reach Maximum Observed Plasma Concentration
TQT	Thorough QT/QTc
TSS	Total Severity Score
ULN	Upper Limit of Normal
US	United States
USA	United States of America
UV	Ultraviolet
UV-B	Ultraviolet B
VAS	Visual Analog Scale

Appendix 2. Diagnostic Criteria for Atopic Dermatitis

Per [Inclusion Criterion 2](#), a subject is to have a clinical diagnosis of atopic dermatitis according to the criteria of Hanifin and Rajka.³¹

Table 8. Hanifin and Rajka's Diagnostic Criteria for Atopic Dermatitis

Major Criteria (must have at least three)
Pruritus
Typical morphology and distribution:
Adults: flexural lichenification or linearity
Children and infants: facial and extensor involvement
Chronic or chronically-relapsing dermatitis
Personal or family history of atopy (asthma, allergic rhinitis, atopic dermatitis)
Minor Criteria (must have at least three)
Xerosis
Ichthyosis/keratosis pilaris/palmar hyperlinearity
Immediate (type 1) skin test reactivity
Elevated serum IgE
Early age of onset
Tendency toward cutaneous infections (esp. staphylococcus aureus and herpes simplex), impaired cell-mediated immunity
Tendency toward non-specific hand or foot dermatitis
Nipple eczema
Cheilitis
Recurrent conjunctivitis
Dennie-Morgan infraorbital fold
Keratoconus
Anterior subcapsular cataracts
Orbital darkening
Facial pallor, facial erythema
Pityriasis alba
Anterior neck folds
Itch when sweating
Intolerance to wool and lipid solvents
Perifollicular accentuation
Food intolerance
Course influenced by environmental and emotional factors
White demographism, delayed blanch

Appendix 3. Very High/Very Strong and High/Strong Potency Topical Corticosteroids

Per [Exclusion Criterion 2](#). Based upon the World Health Organization classification where topical corticosteroids have been ranked in terms of potency into four groups consisting of seven classes.

Including but not limited to;

Very high potency topical corticosteroids

Group 1

- Clobetasol propionate cream (0.05%);
- Diflorasone diacetate ointment (0.05%).

High potency topical corticosteroids

Group II

- Amcinonide ointment (0.1%);
- Betamethasone dipropionate ointment (0.05%);
- Desoximetasone (cream or ointment) (0.025%);
- Fluocinonide (cream, ointment, or gel) (0.05%);
- Halcinonide cream (0.1%).

Group III

- Betamethasone dipropionate cream (0.05%);
- Betamethasone valerate ointment (0.1%);
- Diflorasone diacetate cream (0.05%);
- Triamcinolone acetonide ointment (0.1%).

Appendix 4. Optical Coherence Tomography Sub-Study – A Study of Optical Coherence Tomography and Biomarkers in Subjects ages 2 to <18 years old, with Mild to Moderate Atopic Dermatitis, treated with Crisaborole Ointment, 2% or Crisaborole Vehicle Ointment or Hydrocortisone Butyrate 0.1% Cream applied BID.

1. Introduction

Skin atrophy, characterized by whole skin thinning and damage to the skin barrier, is a common problem in the treatment of AD with TCS.¹ Often, effective treatment with TCS must be limited because of the risk of skin atrophy.¹ To further explore the benefit/risk of crisaborole ointment, 2%, this sub-study aims to evaluate differences in atrophic skin changes across study treatment groups in Cohort 1.

Optical coherence tomography (OCT) is a non-invasive imaging modality conceptually similar to ultrasound but uses near-infrared radiation rather than sound. It has a 2-10 micron depth resolution compared with 100-1,000 micron typical for clinical US; and 1-2 mm imaging depth vs. 10-100 mm for clinical US. It is thus ideal for imaging the surface layers of accessible tissues such as the skin.² OCT imaging will be obtained using the VivoSight OCT scanner, by Michelson Diagnostics, Ltd. in this sub-study to evaluate atrophic changes in epidermal thickness during and after treatment with study investigational product in Cohort 1.

This sub-study also provides an opportunity to explore differences in Transepidermal Water Loss (TEWL) and cutaneous inflammatory and barrier biomarkers associated with AD within the stratum corneum (SC) across treatment groups in Cohort 1.

The Aquaflux device is an evaporimeter that measures water exchange through human skin using the condenser-chamber method. The condenser-chamber method uses a humidity gradient to determine the amount of water diffusing through the SC³. This device will be used in this sub-study to evaluate TEWL during and after treatment at select sub-study centers.

Tape-strips are a minimally invasive method that captures cutaneous inflammatory and barrier biomarkers within the SC, circumventing the need for skin biopsies, especially in the pediatric population. Studies have used proteomic immune assays and messenger ribonucleic acid analyses to evaluate SC biomarkers in tape-strips from AD lesional and non-lesional skin from patients with AD. Expression of AD-associated biomarkers in AD tape-striped skin have been significantly correlated with disease severity (EASI/pruritus) and the functional barrier measure TEWL. Tape-strips will be used in this sub-study to evaluate SC biomarkers from AD lesional and non-lesional skin.

2. Objectives and Endpoints

The primary objective of this sub-study is to evaluate the differences in atrophic changes in epidermal thickness by structural OCT after treatment with crisaborole ointment, 2% or

crisaborole vehicle ointment, or hydrocortisone butyrate 0.1% cream applied BID for 28 days.

The secondary objectives of this sub-study are to evaluate the differences in atrophic change in epidermal thickness, skin biomarkers of AD, and TEWL during the course of treatment and following treatment with crisaborole ointment, 2% or crisaborole vehicle ointment, or hydrocortisone butyrate 0.1% cream applied BID for 28 days.

This sub-study is expected to provide OCT, TEWL, and skin biomarker evidence of the effects of crisaborole ointment and vehicle ointment compared to TCS.

Primary Sub-Study Endpoint:

- Change in epidermal thickness from Baseline/Day 1 to Day 29

Secondary Sub-Study Endpoints:

- Change in epidermal thickness from Baseline/Day 1 to all sub-study time points except Day 29 (Days 8, 15, 22, and 60)
- Intrasubject difference of change in epidermal thickness between the non-lesional target skin site and the OCT AD lesional target skin site from baseline to Days 8, 15, 22, 29 and 60
- Percentage change from Baseline/Day 1 in TEWL at Days 8, 15, 22, 29 and 60
- Change from Baseline/Day 1 in skin biomarkers of AD at Day 15 and Day 29

3. Sub-Study Design

This sub-study will be conducted in selected centers in the United States, the United Kingdom, and in Germany. This sub-study will include approximately 60 subjects from Cohort 1 that are enrolled in the main study (C3291037) from the selected study centers. Subjects may only enroll in the sub-study during the screening phase or at the baseline visit of the main study prior to any sub-study evaluations or procedure. Subjects that do not qualify for the main study may not participate in the sub-study. Based on the randomization schema from the main study, it is expected that the sample size for this sub-study will include approximately 15 subjects in the crisaborole ointment, 2% arm, 15 subjects in the crisaborole vehicle ointment arm, and 30 subjects in the hydrocortisone butyrate 0.1% cream arm. Subjects will follow the main study assessments and visits as per the schedule of activities for the main study but will also follow additional procedures as described in this appendix. Subjects that are in the main study (C3291037) that are not enrolled in the sub-study will not participate in sub-study procedures or evaluations.

The telephone call at Day 60 in the main study is replaced with an in-clinic visit for sub-study participants.

Sub-study Schedule of Activities

The following activities are to be performed in addition to the activities specified for the main study.

Day [relative to start of study treatment (Day 1)]	Within 35 days prior to Day 1	Baseline/ Day 1	Day 8	Day 15	Day 22	Day 29	Day 43	Day 60 ^a
Window			±1 d	±3 d	±3 d	±3 d	±5 d	±3 d
Visit	Screening	Baseline			End of Treatment/ Early Termination			
Sub-study Informed consent, including assent ^b	X	X						
Review of Sub-study Inclusion Criteria	X	X						
Identify and document sub-study target skin sites.		X						
CLINICAL EVALUATION OF AD								
Target skin sites local ISGA		X	X	X	X	X		X
EASI (global) ^c								X
SKIN IMAGING								
OCT images in triplicate at OCT lesional and non-lesional target skin sites		X	X	X	X	X		X
Transepidermal Water Loss ^d at OCT lesional and non-lesional target skin sites		X	X	X	X	X		X
TAPE STRIP BIOMARKER COLLECTION								
Tape strips at tape strips lesional target skin site		X		X		X		
Tape strips at non-lesional target skin site		X						
PHOTOGRAPHY								
Photography of all sub-study target skin sites ^e		X		X		X		

^a Sub-study subjects will be evaluated in clinic.

^b Sub-study subjects may consent during the Screening Phase or at the Baseline visit, prior to any sub-study evaluations or procedures.

^c An EASI assessment will be performed on Day 60 in addition to Days specified in the main protocol (Days 1, 8, 15, 22, 29, and 43)

^d TEWL will be performed only at selected sub-study investigative centers.

^e In addition to photography for the main study, the sub-study target skin sites will be photographed.

5. Subject Eligibility Criteria

Subjects will be enrolled in the sub-study after meeting the eligibility criteria of the main study during the screening phase. Subjects must sign a separate informed consent document for the sub-study and meet the following Inclusion Criteria:

- A. Subject who is enrolled in Cohort 1.
- B. Subject is between the ages of 2 to <18 years.
- C. Subject is able to sit or lie still during the collection of images for approximately 30 minutes per visit for OCT imaging and photography, additional 30 minutes for TEWL (if applicable) measurements and additional 10 minutes for the tape-strips procedure.
- D. Subject has an AD lesional target skin site with a local ISGA score of 2 or 3 at the cubital fossa, that is accessible with the OCT probe head. This target skin site should be a minimum of 3 cm in each diameter. The target skin site must not include the area from which blood is drawn. This site is the OCT AD lesional target skin site.
- E. Subject has a non-lesional target skin site at the left or right volar forearm with a circumference clear of AD at screening and at Baseline/Day 1 that is accessible with the OCT probe head. This target skin site will have a local ISGA score of 0. The target skin site must not include the area from which blood is drawn. This site is the non-lesional target skin site.
- F. Subject has an AD lesional target skin site separate, but preferably adjacent to the AD lesional target skin site area for tape-strips procedure. This area will also have a local ISGA score of 2 or 3 and will be a minimum of 3 cm in each diameter. If there are not two adjacent lesional target skin sites for OCT and tape-strips, an alternate location for tape strips may be located at an AD lesional target skin site bilateral to the OCT lesional target skin site. The target skin site should not include the area from which blood is drawn. This site is the tape strips AD lesional target skin site.
- G. Evidence of a personally signed and dated informed consent/assent document indicating that the subject or parent(s)/legal guardian has been informed of all pertinent aspects of the sub-study.

6. Sub-Study Procedures

While the Day 60 visit for non-sub-study participants is completed via telephone, the Day 60 visit for subjects enrolled in the sub-study will be completed by a clinic visit to accommodate sub-study procedures.

Identification of target skin sites for OCT and biomarker tape strips

Target skin sites for all sub-study procedures will be identified prior to any sub-study evaluations by the blinded assessor that will also perform the assessments. Target skin sites

will not have striae or other signs of prior TCS treatment. They must not involve the area from which blood is drawn.

1. The **OCT AD lesional target skin site** at the cubital fossa will have a local ISGA score of 2 or 3 and will be accessible with the OCT probe head. The same target skin site will be used for all evaluations throughout the duration of the sub-study. This target skin site will be recorded on a sub-study body map for reference so that the location is used consistently for all subsequent evaluations. This area should be ≥ 3 cm in each diameter.
2. The **non-lesional target skin site** will be at the left or right volar forearm and will be accessible with the OCT probe head. This target skin site must not include the area from which blood is drawn. This target skin site will have a local ISGA score of 0. In choosing between the right and left volar forearm, the side furthest away from any signs of AD should be selected. The same target skin site will be used for all evaluations throughout the duration of the sub-study. This target skin site will be recorded on a sub-study body map for reference so that the location is used consistently for all subsequent imaging. This area should be ≥ 3 cm in each diameter.
3. The **tape-strips lesional target skin site** will preferably be adjacent to the AD lesional target skin site and will have a local ISGA score of 2 or 3. If there are not two adjacent target skin sites for OCT and tape-strips, an alternate location for tape-strips may be located at the site bilateral to the OCT target skin site. The same target skin site will be used for all tape-strip collections throughout the duration of the sub-study. This target skin site will be recorded on a sub-study body map for reference so that the location is used consistently for all subsequent collections. This area should be ≥ 3 cm in each diameter without overlapping with the AD lesional target skin site.

Treatment of target skin sites

The OCT AD lesional target skin site and the tape-strips AD lesional target skin site will be included in the main study treatment area and will be treated for 28 days with investigational product even if the AD resolves during the course of treatment.

The non-lesional target skin site at the volar forearm will be free of AD, however this area will be treated with investigational product for the duration of the 28-day treatment period.

Treatment with investigational product on all target skin sites should be withheld on all study visit days until after the study visit procedures. The time since last investigational product treatment of the target skin sites and the time of study visit procedures will be collected.

Local ISGA score

A local target ISGA score will be obtained and recorded for all three target skin sites on Baseline/Day 1, Day 8, Day 15, Day 22, Day 29, and Day 60 in addition to the overall ISGA.

EASI assessment

An EASI assessment will be performed on Day 60 in addition to the Days specified in the main protocol (Baseline/Day 1, Day 8, Day 15, Day 22, Day 29 and Day 43).

Photography of target skin sites

Each sub-study target skin site will be photographed in addition to any photography performed for the main study at Baseline/Day 1, Day 15, and Day 29. Each photograph will be labeled with the corresponding target skin site.

OCT measurements, TEWL, and Tape-strips

Technical detail and set-up of the OCT measurements, TEWL, and the tape-strip procedure will be provided to participating centers in Laboratory Manuals. All sub-study evaluations will be completed after and in addition to main study procedures completed at those clinic visits. Both the operator and the accessor of images will be blinded. OCT measurements will be obtained first, followed by TEWL (if applicable) at OCT AD lesional and non-lesional target skin sites. Tape-strips for biomarkers will be conducted after OCT and TEWL measurements at the tape-strips target skin site.

Both the OCT AD lesional target skin site and the non-lesional target skin site will be imaged by OCT in triplicate on Baseline/Day 1, Day 8, Day 15, Day 22, Day 29, and Day 60. The operator should be consistent across all imaging taken for each individual subject. An Imaging partner will be responsible for standardizing the OCT image acquisition, training the centers on the imaging protocol, ensuring equipment and image quality assurance and quality control. Image analysis will be conducted by a central reader(s) who will be blinded. Detailed procedures for obtaining and processing the OCT image, conducting image quality assurance/quality control and endpoint analyses will be described in study specific documents and provided as appropriate to the study centers.

TEWL will be measured at both the OCT AD lesional target skin site and the non-lesional target skin site (not at the tape-strips lesional target skin site) on Baseline/Day 1, Day 8, Day 15, Day 22, Day 29, and Day 60 at selected sub-study centers. The operator should be consistent across all measurements taken for each individual subject.

Tape-strips for biomarker collection will be completed at the non-lesional target skin site on Baseline/Day 1 only. Tape-strips for biomarker collection will be completed at the tape-strips lesional target skin site on Baseline/Day 1, Day 15, and Day 29. The operator should be consistent across all tape-strip collections for each individual subject. The operator will be blinded. A tape strips biomarker partner will be responsible for standardizing the collection and analysis of biomarkers. Detailed procedures for biomarker collection, processing and analysis will be described in a separate document and provided to the study centers.

Prior and concomitant treatments

Prior and concomitant topical treatments (per section 5.8) used on sub-study target skin sites will be recorded in the CRF. In addition to restrictions regarding concomitant medications described in section 5.8.4 of protocol, all effort should be made to not apply AD treatments to sub-study defined target skin sites after the treatment phase until the Day 60, End of Study Visit, even if other lesions are necessary to treat with concurrent treatment for AD.

7. Data Analysis/Statistical Methods

Approximately 60 subjects (15, 15, 30 in vehicle, crisaborole, hydrocortisone groups respectively) will participate this sub-study from Cohort 1. This sub-study is a pilot and there is no formal hypothesis testing. The sample size is not based on a power calculation and an estimation approach will be used for data analysis and interpretation.

The analysis of change from baseline to Day 8, Day 15, Day 22, Day 29, and Day 60 in epidermal skin thickness, will be analyzed using mixed model repeated measure (MMRM) with treatment, visit, treatment by visit interaction as factors and baseline value as a covariate, separately for OCT AD lesional target skin site and non-lesional target skin site. Within-subject variability will be accounted for using a random effect with the first order autoregressive (AR(1)) covariance matrix.

The same models as above will be used for percentage change from baseline in TEWL at Baseline/Day 1, Day 8, Day 15, Day 22, Day 29 and Day 60. No baseline value will be included as a covariate in the model.

Intra-subject difference of change from baseline to Day 8, Day 15, Day 22, Day 29, and Day 60 in epidermal skin thickness between OCT AD lesional target skin site and non-lesional target skin site will be analyzed using MMRM model with visit as a factor for each treatment group.

For the tape-strip biomarkers, Log2-scale quantitative reverse transcription polymerase chain reaction expression data will be modeled by a linear mixed effect model with visit, treatment, visit by treatment interaction as fixed effects and a random effect for each subject. Means of each group will be estimated using least squares means and comparisons of interest will be tested using contrast.

This sub-study will be reported independently from the main Clinical Study Report.

References

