2.2. Study Design

This is a Phase 3b/4, multicenter, randomized, assessor blinded, vehicle and active (topical corticosteroid [TCS] and topical calcineurin inhibitor [TCI]) controlled study of the efficacy, safety and local tolerability of crisaborole ointment, 2% in pediatric and adult subjects, ages 2 years and older, with mild to moderate AD involving at least 5% treatable body surface area (%BSA). Treatment will be clinical assessor blinded for all treatment arms and double blinded for crisaborole ointment, 2% and vehicle treatment arms.

A total of approximately 600 subjects will be enrolled in the study, of which at least 150 subjects aged 2-6; at least 140 subjects aged 7-11; at least 120 subjects aged 12-17, and up to 90 subjects will be adults. Following the screening period (up to 35 days prior to Baseline/Day 1), eligible subjects will be randomized at the Baseline/Day 1 visit.

Randomization will be stratified by eligibility for TCS or TCI treatment as per national approved labels and eligibility provided in Section 4 of the protocol. Cohort 1 will be for subjects who are eligible for TCS therapy, and Cohort 2 will be for subjects who are not eligible for TCS therapy but eligible for TCI therapy. The investigational product will be applied BID for 28 days to the Treatable BSA identified at Baseline/Day 1. Any new AD on treatment eligible locations occurring following Baseline/Day 1 should also be treated with the study drug after consultation with the Investigator at the next visit.

The primary efficacy endpoint is the percent change from baseline in the EASI total score at Day 29.

For the efficacy comparison of crisaborole versus vehicle, subjects from both Cohort 1 and Cohort 2 are included in the analysis, adjusted for cohort effect. For the efficacy comparison of crisaborole versus TCS, only subjects from Cohort 1 are included in the analysis. For the comparison of crisaborole versus TCI, only subjects from Cohort 2 are included in the analysis.

[figure not shown]
Safety and efficacy assessments will be conducted at the investigator site by a clinical assessor blinded for treatment arms.

A sub-study will be conducted at selected investigator sites to evaluate differences of changes in epidermal skin thickness as measured by Optical Coherence Tomography (OCT) between treatment groups in Cohort 1. Detailed statistical analysis for sub-study will be given in a separate SAP.

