5.1. Hypotheses and Decision Rules

This study was terminated. The termination decision was made for business reasons only and was not related to any safety or efficacy concerns regarding crisaborole. Only 40% of planned participants were enrolled at termination. Due to small sample size, no hypotheses testing and decision rules. No statistical analysis and comparison will be performed. Only descriptive summary will be generated for safety data and some efficacy endpoints.

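### The OCT sub-study's TEWL model takes Baseline/Day 1 as a response visit, where percent change is always 0; under assumed correlations this lowers the AR(1) standard error at Day 29 by about 9–16%

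*Protocol*

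**What the plan says.** Appendix 4 of the Protocol gives three visit lists that bear on the TEWL analysis:

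- Section 2 (endpoints): "Percentage change from Baseline/Day 1 in TEWL at Days 8, 15, 22, 29 and 60". Five visits.
- Section 7 (thickness model): "The analysis of change from baseline to Day 8, Day 15, Day 22, Day 29, and Day 60 in epidermal skin thickness". Five visits. The model has treatment, visit and their interaction, a baseline covariate and an AR(1) covariance.
- Section 7 (TEWL model, which reuses the thickness model): "percentage change from baseline in TEWL at Baseline/Day 1, Day 8, Day 15, Day 22, Day 29 and Day 60". Six visits.

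The sentence after the TEWL list adds: "No baseline value will be included as a covariate in the model".

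The six-visit list is the same as the measurement schedule in section 6, where TEWL is taken "on Baseline/Day 1, Day 8, Day 15, Day 22, Day 29, and Day 60 at selected sub-study centers". The sub-study is a pilot without hypothesis tests, and section 7 says "an estimation approach will be used for data analysis and interpretation". SAP section 2.2 adds: "Detailed statistical analysis for sub-study will be given in a separate SAP". That document was not available for this review.

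**The concern.** Baseline TEWL is the denominator of the percent change, so it has to be measured on Day 1. It is not an outcome on Day 1: the percent change there is 0 for every subject in every arm. Because baseline is also ruled out as a covariate, the only role left for Baseline/Day 1 in the model as written is that of a response.

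This does harm because AR(1) assumes the same variance at every visit. A visit with variance exactly zero is averaged into that common variance and lowers it, and the standard error at Days 8 to 60 falls with it, although no information has been added. In a sub-study that only estimates, the precision attached to each TEWL difference is part of the result.

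**Working it through.** The plan states no standard error, SD or power figure for TEWL, so there is no figure of its own to reproduce. The check compares the stated model with and without the Day 1 visit.

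**Inputs from the documents (Appendix 4, section 7):** arm-by-visit means, AR(1) covariance, no baseline covariate, and 15 vehicle, 15 crisaborole and 30 hydrocortisone butyrate subjects.

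**Assumed, because the documents do not give them:** complete data; correlation r between adjacent visits from 0 to 0.85; the pattern of SDs over visits; t intervals with N − 3 degrees of freedom.

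**Step 1. Reduce the question to one ratio.** With treatment-by-visit means and complete data, the estimated difference at Day 29 is the difference in observed arm means, so adding a visit does not change it. Its standard error is σ̂·√(1/n₁ + 1/n₂). The effect of the zero visit is therefore σ̂(six visits) / σ̂(five visits).

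**Step 2. Fit the common variance, constant SD.** Set the true SD at Days 8 to 60 to 1. Given a fitted AR(1) correlation ρ, the variance estimates are:

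- five visits: σ̂² = (5 − 8rρ + 3ρ²) / [5(1 − ρ²)]. The fit gives ρ = r and σ̂² = 1, which is correct.
- six visits, Day 1 all zero: σ̂² = (5 − 8rρ + 4ρ²) / [6(1 − ρ²)], with ρ chosen to minimise 6·log(σ̂²) + 5·log(1 − ρ²).

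Example, r = 0.5: the minimum is at ρ = 0.416, so σ̂² = (5 − 1.664 + 0.692) / (6 × 0.827) = 4.028 / 4.962 = 0.812, and √0.812 = 0.901.

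| r | fitted ρ | σ̂² | SE ratio | SE reduction |
|---|---|---|---|---|
| 0 | 0 | 5/6 = 0.833 | 0.913 | 8.7% |
| 0.5 | 0.416 | 0.812 | 0.901 | 9.9% |
| 0.7 | 0.585 | 0.784 | 0.885 | 11.5% |
| 0.85 | 0.716 | 0.747 | 0.864 | 13.6% |

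At r = 0.95 the reduction is 16.0%. Simulation with 15/15/30 subjects gives the same mean reductions at 0, 0.5, 0.7 and 0.95. With 15% dropout it gives 9.7–13.7% for r from 0.3 to 0.9.

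**Step 3. Let the SD vary over Days 8/15/22/29/60** (large-sample fit, r from 0 to 0.85). The last two columns divide the model SE at Day 29 by the true SE.

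| SD pattern | SE reduction from zero visit | model/true, with visit | model/true, without |
|---|---|---|---|
| constant 34 | 8.7–13.6% | 0.86–0.91 | 1.00 |
| rising 28/30/32/34/34 | 8.7–12.2% | 0.81–0.85 | 0.92–0.93 |
| rising 24/28/31/34/34 | 8.7–11.0% | 0.78–0.82 | 0.88–0.90 |
| falling 38/36/33/30/30 | 8.7–15.1% | 0.96–1.02 | 1.12–1.13 |
| falling 40/37/34/30/34 | 8.7–15.8% | 1.02–1.07 | 1.17–1.21 |

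**Step 4. What this does to an interval (constant SD, crisaborole v hydrocortisone, Day 29).**

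- 15/15/30: the correct half-width is t(57)·√(1/15 + 1/30) = 2.002 × 0.316 = 0.633 SD. Multiplied by 0.864 to 0.913, it is reported as 0.55–0.58 SD. Coverage is P(|t₅₇| < 0.864 × 2.002) = 91.1% up to P(|t₅₇| < 0.913 × 2.002) = 92.7%. Simulation gave 91.6–93.1% with the visit and 95.2–95.8% without.
- SAP section 5.1 says "Only 40% of planned participants were enrolled at termination". If the sub-study stopped in the same proportion (an assumption), the arms are 0.4 × 15/15/30 = 6/6/12. The correct half-width is then 2.080 × √(1/6 + 1/12) = 1.040 SD, reported as 0.90–0.95 SD.

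**The case against.** The intent can be recovered: the endpoint list has five visits, the model being reused has five visits, and the sixth looks like a slip copied from the measurement schedule. The detailed analysis belongs to a sub-study SAP that may already be right. After termination the main SAP dropped modelling altogether, so no available document shows that this model would be fitted.

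The size is also conditional. The documents give neither the correlation nor the SD pattern of TEWL percent change. Within r up to 0.85, reductions above 13.6% occur only with falling SDs. In those patterns the standard error with the zero visit is close to the truth, and deleting the visit moves it further away, to 1.12–1.21 times the true value. The number of subjects with TEWL is unknown too, because it is measured only at selected centers, so the coverage and half-width figures are illustrative.

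Most of this stands as a limit on size and consequence, and it should be stated with the result. It does not rescue the wording. A response that is zero by definition cannot be justified by the chance that its error offsets a different one, namely a common variance imposed on unequal variances. With rising SDs the two errors add up instead. The contradiction between sections 2 and 7 remains whatever the sub-study SAP says.

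**Conclusion.** The concern holds. The TEWL sentence in section 7 of Appendix 4 contradicts the endpoint list in section 2 and makes a structural zero part of the response. Under the AR(1) model as written, this lowers the Day 29 standard error by about 9–16% relative to the same model on five visits, for correlations of 0 to 0.85 and the five SD patterns tried. With constant SD the range is 8.7–13.6%, and a nominal 95% interval covers about 91–93%. Whether the standard error would be too small overall depends on how TEWL variability changes over visits, which the documents do not give.

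The scope is narrow: one secondary endpoint at selected centers in a pilot, with complete-data point estimates and all main-study results unaffected. The conflict in wording is certain. An effect on reported results is not, because the sub-study SAP could not be seen. The correction should be made, but it is not critical.

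**What to change.** In section 7 of Protocol Appendix 4, delete Baseline/Day 1 from the visit list in the TEWL sentence, leaving Days 8, 15, 22, 29 and 60, as in the endpoint list in section 2. Use the same five visits in the separate sub-study SAP; if it already does so, only the protocol text needs correcting. No other change to the model is requested.

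The cost is wording only. Day 1 TEWL is still measured, because every percent change is computed from it, and no visit, procedure or data item changes.
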